## **BoneFit: A Student-Led Multimodal Prehabilitation Service for Orthopaedic Surgical Patients in Hull**

### **Introduction:**

In the UK, there are >8 million surgical operations performed every year, and this is likely to continue to rise due to the increasing ageing population [1,2]. Surgery can lead to reduction in physical function, a loss of independence due to continued bed rest and deconditioning, increased pain and discomfort, and can lead to physical and mental complications including increased stress, anxiety and depression. These symptoms can lead to higher readmission rates and longer hospital stays [3].

Due to the recent global pandemic, surgical procedures were cancelled *en masse* leading to increasing waiting lists and, at an individual level, continued deconditioning and an increasing risk of functional limitations particularly in the elderly. In the UK, prehabilitation is a single component of Early Recovery After Surgery (ERAS), a multi-step treatment package designed to help prepare individuals for the physical and mental insult of surgery. Being able to optimise an individual prior to surgery is likely to lead to improved patient outcomes and should save the NHS money by reducing the length of hospital stay, complications and readmission rates [4]. Prehabilitation interventions have evolved over the years becoming multimodal in nature. Interventions typically include exercise, nutrition, and psychological support delivered by a multidisciplinary team [5].

In people receiving orthopaedic surgery, the evidence-base showing the positive impact of prehabilitation continues to grow. In 2023, a large-scale systematic review and meta-analysis based on 48 unique trials involving 3,570 participants (61.5% female, mean age 64 years) reported level I moderate-certainty evidence

supporting prehabilitation versus usual-care for improving pre-operative function and strength in people undergoing total knee replacement (TKR) surgery, and moderate-certainty evidence for increased health-related quality of life (HRQoL) and muscle strength for individuals undergoing total hip replacement (THR) surgery [6].

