### **Study Start and End-dates**

The study is planned to run from March/April 2024 to July 2027. We plan to recruit 50 patients and controls (25 per group). Once these numbers have been achieved we will cease recruitment and just continue with the follow-up visits (final follow up is 12 months following surgery).

- **Inclusion criteria:**

Age 18-75 years;

Waiting for unilateral TKR or THR surgery for a minimum of 6 months;

Able to provide informed consent;

- **Exclusion criteria:**

Previous TKR/THR surgery;

Any medical conditions for which moderate to vigorous exercise is contraindicated;

Patellar or hip joint instability;

Any other disease/condition which severely effects functional performance e.g. stroke or Parkinson's disease;

Age <18 years or >75 years;

No access to smartphone or home internet;

Chronic depression or significant psychiatric disorder;

Enrolled in a clinical trial (or recently completed one);

Cognitive impairment which would affect compliance to BoneFit service;

Patients unable or unwilling to commit to required study follow-ups and unwillingness to work with students;

Pregnancy;

- **UoH Student-Led PCPs:**

All students will work under the guidance of a qualified professional based at the UoH. Multimodal prehabilitation involves the core disciplines of exercise, nutrition and clinical psychology. Therefore, students involved in the following programmes will help supply PCPs as part of their student placements, projects/dissertations or as part of an internship:

- BSc Physiotherapy
- BSc Sports Rehabilitation
- MSc Dietetics
- BSc Sports Nutrition
- MSc Clinical Exercise Physiology
- MSc Cardiovascular Rehabilitation
- Clinical Psychology Doctorate

- **Service Design:**

Following guidance from the 2019 NHS Long Term Plan (<https://www.longtermplan.nhs.uk/>) we will use a personalised approach when developing the PCPs. Validated screening and assessment tools will enable assignment of participants. Those with no increased risk factors and with no increased surgical risk will receive **universal support**. Further assessment will be undertaken for those requiring more than universal support and they will be allocated to **targeted** (intermediate risk/needs) or **specialist** (high risk/complex needs). Patients may receive different levels of support for the different intervention components: exercise, nutrition and psychological support.

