**Controls (usual care):** In a non-randomised manner, we will identify a group of age- and sex-matched individuals referred for hip (THR) or knee replacement (TKR) surgery from patients who contact the BoneFit service. PIS forms will be circulated by clinical staff to eligible patients awaiting TKR/THR surgery in their routine clinic at Castle Hill Hospital. Interested parties will contact the BoneFit service for more information. If patients agree to participate they will be invited to the University of Hull to provide consent and will undertake a series of baseline assessments and will be allocated by BoneFit staff to the intervention or control group at this point.

Current HUTH waiting list times for orthopaedic surgery is <18 months. Following referral, patients will be asked to complete DASI, download the (enhanced recovery after surgery (ERAS+) app onto their smartphones and follow its guidance. If they do not have access to a smartphone, they will be referred to the ERAS+ website, or if they have no internet connection, hard copies of generic guidance will be posted to them. At the 2-month point prior to surgery, they will be referred to the Hip-Hub for further evaluation and to receive their PCPs.

The Hip-Hub (<https://hiphub.hull.ac.uk/>)- the UoH sports injuries clinic will manage the patient referral process and BoneFit will benefit from existing referral, data management, facilities, equipment, and communication systems. Referred patients will initially be contacted by Hip-Hub staff and invited to attend for an initial screening session (see Screening, Assessment and Outcomes sections below). Validated screening tools and outcome measures will be used to determine the type of PCP required, and patient data will be recorded. The type of intervention received will depend on whether a patient requires universal, targeted or specialist PCPs. Students will stay in regular contact with patients to ascertain fidelity and compliance with the PCP.

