All students will be working under the support and guidance of trained clinical professionals in physiotherapy, sports therapy, nutrition/dietetics, and clinical psychology or clinical exercise physiology. Student-patient interactions will be delivered either in a face-to-face individual or group setting, virtual (one-to-one or group-based using Teams or equivalent) or via telephone. Sessions will mainly be delivered live although some pre-recorded material will be used to supplement live sessions and an online resources library will be built up over time.

Outcome measures for each of the three core components (exercise, nutrition and clinical psychology) will be evaluated at 5 timepoints (initial surgical referral e.g. 18 months from surgery; baseline [2 months from surgery], immediately prior to surgery [2 to 10 days], and 3 and 12 months after surgery). See Table 1 to identify which outcome measures will be recorded. At initial surgical referral, DASI will be completed remotely. However, the remaining 4 timepoints will require face-to-face interactions and more in-depth investigations.

**Table 1.** Outcome and timepoints assessments for individuals recruited to BoneFit

Variable/ Timepoint	2 months from surgery	2-10 days prior to surgery	3 months post op	12 months post op
Physical/ Exercise				
DASI	✓		✓	✓
ISWT	✓	✓	✓	✓
Timed up and go	✓	✓	✓	✓
Hand-grip strength	✓	✓	✓	✓
HOOS-12 or KOOS-12	✓	✓	✓	✓
Nutrition				
MUST	✓	✓	✓	✓
PG-SGA	✓	✓	✓	✓
Clinical Psychology				
EQ-5D-5L (QoL)	✓	✓	✓	✓

GAD-7	✓	✓	✓	✓
PHQ-9	✓	✓	✓	✓
Emotions thermometer	✓	✓	✓	✓
Clinical outcomes				
Length of hospital stay			✓	✓
Complications			✓	✓
Re-admission rates			✓	✓
VAS pain scale	✓	✓	✓	✓

DASI - Duke Activity Score Index; ISWT: incremental shuttle walk test; VAS: visual analogue scale; MUST: malnutrition universal screening tool; PG-SGA: patient-generated global assessment; GAD-7: generalised anxiety disorder assessment; PHQ-9: depression test score; EQ-5D-5L: health and quality of life questionnaire; HOOS-12: hip disability and osteoarthritis outcome score-12; KOOS-12: knee injury and osteoarthritis outcome score-12.

At initial surgical referral, all participants referred for BoneFit will receive existing ERAS guidance on developing healthier lifestyle choices in preparation for surgery

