### **Sample Size and Process Evaluation:**

Feasibility studies are typically unpowered, based on similar studies, we will aim to recruit 25 participants to the BoneFit intervention and 25 usual-care controls (n=50).

A concurrent mixed methods process evaluation will explore safety, implementation, delivery, and acceptability of the intervention. We will use semi-structured interviews with participants and practitioners along with process data to assess:

- Barriers to recruitment;
- Acceptability and adherence to the intervention (dose received);
- Intervention delivery (fidelity);
- How the intervention was embedded into clinical practice;
- Safety outcomes: will include adverse events and serious adverse events;
- We will collect quantitative process data on safety, screening and recruitment, fidelity and dose/drop-out which will enable discussions with clinical teams to identify remedial actions to improve recruitment, retention, and fidelity.

We will conduct a pilot feasibility study of the BoneFit intervention which will take approximately 3 years to complete (including all 12-month follow up visits).

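### Controls are matched on age and sex but not on operation, so the secondary comparisons with usual care may be confounded by hip versus knee replacement

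*Protocol*

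**What the plan says.** All references are to the protocol.

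- **Eligibility.** The inclusion criteria admit both operations: "Waiting for unilateral TKR or THR surgery for a minimum of 6 months". No quota or stratum by joint is given.
- **Matching.** The paragraph on usual-care controls reads: "In a non-randomised manner, we will identify a group of age- and sex-matched individuals referred for hip (THR) or knee replacement (TKR) surgery". Age and sex are the matching factors. The reference to hip or knee replacement describes the pool from which controls come.
- **Allocation.** In the same paragraph, patients who consent and complete baseline assessments "will be allocated by BoneFit staff to the intervention or control group at this point".
- **Outcomes.** Table 1 has a single row, "HOOS-12 or KOOS-12", ticked at all four face-to-face timepoints. Its footnote defines the hip and knee instruments separately: "HOOS-12: hip disability and osteoarthritis outcome score-12; KOOS-12: knee injury and osteoarthritis outcome score-12".
- **Comparisons.** The secondary objectives under Study Outcomes look for an efficacy signal in physical health, mental wellbeing and quality of life, and for differences in DASI, length of stay, complications and readmissions. All are against usual care, and the two operations are not separated.
- **Size and primary outcome.** Sample Size and Process Evaluation gives 25 participants per group and treats the study as unpowered. The primary outcomes are feasibility and acceptability.

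**The concern.** In a non-randomised comparison, matching is the only design feature described that makes the groups alike. The operation is known at referral and is an obvious candidate prognostic factor: joint function, walking, pain and length of stay could all follow the joint replaced. It is nevertheless left out of the matching, and staff choose the group without any stated constraint on the joint mix. If one group ends up with more hip patients, part of any difference from usual care could reflect the operation rather than prehabilitation. An apparent benefit could be created or hidden in this way.

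The secondary results matter beyond description. Under Anticipated impact, the protocol says that further funding will be sought if the pathway succeeds in improving patient outcomes. Matching factors also act at enrolment, so a later analysis plan cannot change who was placed in which group.

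**Working it through.** **The plan's own figure.** The protocol gives no alpha, power, effect size or SD, so only the total can be checked: 25 + 25 = 50, as stated.

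**Inputs**
- From the protocol: 25 per group; matching on age and sex; non-randomised allocation by staff.
- Assumed, because the protocol gives neither: the share of one operation in the recruited pool (0.3 to 0.6, with 0.5 as the central case), and the hip-knee difference in an outcome (0.2, 0.5 or 0.8 SD).

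**Step 1. How large could the imbalance be?** As a benchmark, treat allocation as random with respect to joint, so that the two groups give independent Binomial(25, p) counts.

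SD of the difference in share at p = 0.5: sqrt(2 × 0.25 / 25) = 0.141, or 14 percentage points.

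| Assumed share p | P(difference ≥ 3 patients, 12 points) | P(≥ 5 patients, 20 points) | P(≥ 7 patients, 28 points) | Mean absolute difference (patients) |
|---|---|---|---|---|
| 0.3 | 0.440 | 0.164 | 0.044 | 2.6 |
| 0.4 | 0.471 | 0.193 | 0.059 | 2.7 |
| 0.5 | 0.480 | 0.203 | 0.065 | 2.8 |
| 0.6 | 0.471 | 0.193 | 0.059 | 2.7 |

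The result depends little on p. Staff allocation is not a chance mechanism, so the true imbalance could be smaller or larger than these figures suggest.

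**Step 2. What bias follows?** For an unadjusted difference:

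bias (SD) = difference in joint share between groups × hip-knee difference (SD)

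| Imbalance in share | Hip-knee 0.2 SD | 0.5 SD | 0.8 SD |
|---|---|---|---|
| 0 | 0 | 0 | 0 |
| 20 points | 0.04 | 0.10 | 0.16 |
| 40 points | 0.08 | 0.20 | 0.32 |

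**Step 3. Compare with sampling error.** With all 25 per group observed, the standard error of a group difference is sqrt(2/25) = 0.283 SD. At a 20-point imbalance the bias is therefore 0.04/0.283 = 0.14 to 0.16/0.283 = 0.57 standard errors.

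**Step 4. What do the remedies achieve?** Equal joint mix in both groups makes this bias zero at n = 50. Stratifying by operation without matching also removes it, at some cost in precision. When the second group has the reverse mix of the first, the stratified standard error is sqrt((1/a + 1/b)/2), where a and b are the numbers of hip and knee patients in one group:

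- equal mix (12.5 and 12.5): 0.283 SD
- 60/40 against 40/60 (15 and 10): 0.289 SD
- 70/30 against 30/70 (17.5 and 7.5): 0.309 SD

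Neither remedy needs a larger sample.

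**The case against.** The strongest case against has five parts.

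1. **The analysis can deal with it.** Stratifying or adjusting for operation removes the bias, and it may already be in a statistical analysis plan that is not shown. This stands in part. Adjustment loses little at moderate imbalance (0.289 against 0.283 SD), so matching is not the only repair. But the choice of matching factors is made in the protocol, and in a lopsided sample one joint could have too few patients in one group to compare.

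2. **The single Table 1 row proves nothing.** A reader might infer from it that hip and knee scores will be averaged together. The protocol does not say so. Table 1 is an assessment schedule, the row is naturally read as each patient completing the form for the operated joint, and reporting by joint can properly be left to the analysis plan. This objection stands in full.

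3. **The Introduction does not show that the operations differ in prognosis.** The cited review supports prehabilitation for function and strength in knee patients, and for quality of life and strength in hip patients. A reader might take this as evidence that joint drives outcome. It shows only where evidence of benefit was found. Even a true difference in benefit would be effect modification, not the prognostic difference that confounding needs. This stands, and the point does not rely on that evidence.

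4. **The stakes are limited.** The comparisons are secondary in an unpowered feasibility study, and operation is one of several unmatched factors under staff allocation. This stands as a limit on importance. The point is still distinct from how allocation is done: simple randomisation without stratification would also leave the joint mix to chance.

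5. **A third factor has a cost.** Controls come from patients who contact the service, and recruitment is itself a feasibility measure. This stands and is counted under the fix.

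**Conclusion.** The point holds as a risk: the secondary comparisons with usual care may be confounded by operation if the hip/knee mix differs between groups, and the protocol does nothing at enrolment to prevent that. A reader might go further and conclude that the group differences do mix joint with treatment. The documents do not support this, because no imbalance is shown and confounding requires one.

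The likely size is modest. A 20-point imbalance has about a 16% to 20% chance under the benchmark and gives a bias of 0.04 to 0.16 SD, below the standard error of 0.28 SD. Larger biases need a larger imbalance, which chance rarely produces but which staff allocation does not rule out. These figures rest on an assumed joint mix, an assumed hip-knee difference, chance allocation as a stand-in for the staff's choice, and complete follow-up.

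The feasibility and acceptability outcomes are untouched. The change is worth making because it is cheap and must be made before patients are allocated.

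**What to change.** In the paragraph on usual-care controls, add operation (THR or TKR) as a matching factor beside age and sex. State there that, if an exact match on operation cannot be found, the between-group difference will be estimated stratified by, or adjusted for, operation.

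This needs no new data, visits or participants, since the operation is known before allocation. Matches become slightly harder to find with 25 per group, which may slow recruitment a little. If matching fails and stratification is used instead, the loss of precision is small unless the mix is very uneven (Step 4 of the working). The change removes confounding by operation only; it does not answer other differences that non-randomised allocation may leave between the groups.

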## **Study Outcomes:**

- Primary objective**

The primary outcome measures are feasibility and acceptability of the BoneFit intervention. Feasibility will be assessed by determining the number of participants recruited, trained and retained at the end of the intervention, the proportion of intervention sessions delivered and fidelity of delivery. Moreover, participant recruitment, retention and adherence to the intervention will be measured, as well as any adverse events. To determine the acceptability of the intervention and to explore barriers and enablers to the implementation of the intervention, interviews will be conducted amongst participants (n=6), and staff involved in referral and intervention delivery (n=6) (see process evaluation below).

- Secondary objectives**

- To identify a signal of efficacy for positive changes in physical health (exercise and nutrition), mental wellbeing, and quality of life (using tools described below) compared to usual care;
- To identify differences in DASI, length of hospital stay, complications and readmission rates to hospital following orthopaedic surgery (initially TKR and THR procedures) compared to usual care;
- Assess surgeons' and surgical practitioners' willingness to refer to BoneFit;
- Assess participants experiences of the BoneFit intervention;

### **Sample Size and Process Evaluation:**

Feasibility studies are typically unpowered, based on similar studies, we will aim to recruit 25 participants to the BoneFit intervention and 25 usual-care controls (n=50).

A concurrent mixed methods process evaluation will explore safety, implementation, delivery, and acceptability of the intervention. We will use semi-structured interviews with participants and practitioners along with process data to assess:

- Barriers to recruitment;
- Acceptability and adherence to the intervention (dose received);
- Intervention delivery (fidelity);
- How the intervention was embedded into clinical practice;
- Safety outcomes: will include adverse events and serious adverse events;
- We will collect quantitative process data on safety, screening and recruitment, fidelity and dose/drop-out which will enable discussions with clinical teams to identify remedial actions to improve recruitment, retention, and fidelity.

We will conduct a pilot feasibility study of the BoneFit intervention which will take approximately 3 years to complete (including all 12-month follow up visits).

### **Screening and Assessment for Exercise/Fitness/Functional Capacity:**

Screening: We will use the Duke Activity Status Index (DASI) [7] to screen for reduced functional capacity. Patients with a DASI score > 34 are at low risk and will be assigned to **universal support**, those with a DASI score <34 will be referred for an assessment.

Assessment: An incremental shuttle walk test (ISWT)[8] will be performed to assess patients' functional capacity. Patients with ISWT distance of <475m will be assigned to **targeted** intervention. Patients with a ISWT distance of <400m or patients with a medical comorbidity that necessitates supervised exercise will be assigned to **specialist** intervention. If a patient is deemed unsuitable to complete the ISWT by the clinical supervisor due to functional limitations or progressive pain, we will ask them to just undertake a Timed Up and Go test and use this to screen into targeted (<18 seconds), or specialist groups (>=18 seconds).

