**Aims:** The aim of BoneFit is to provide local people living in the Hull region with a needs-based prehabilitation care package (PCP) to improve their physical and mental health, quality of life & reduce their length of hospital stay, complications and readmission rates to hospital following orthopaedic surgery (initially TKR and THR procedures).

Currently, Hull University Teaching Hospitals (HUTH) do not offer a prehabilitation/ERAS service for local patients. The University of Hull (UoH) will partner with HUTH to provide a student-led multimodal prehabilitation service for referred patients awaiting orthopaedic surgery (initially TKR or THR). This is a proof-of-concept trial where external funding will be applied for to underpin and expand the service to support other specialities, if shown to be successful.

Only low-to-moderate risk patients will be initially referred to receive a PCP (risk score between 0 to 6). Patients who score  $\geq 7$  points on the operative risk estimation chart will not be referred (see final page of the GP referral form for full details of risk criteria).

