### **Screening and Assessment for Psychological Status:**

Screening: Patients will be screened using the General Anxiety Disorder Assessment (GAD-7) [12], the Patient Health Questionnaire 9 (PHQ-9) [13] and the 'need for help' emotions thermometer [14]. Patients scoring <9 on the GAD-7 or PHQ-9 and/ or <5 on the 'need for help' item of the emotions thermometer will be assigned to **universal support**.

Assessment: Patients scoring >9 on the GAD-7 or PHQ-9, and/or >5 on the 'need for help' item of the emotions thermometer will be invited to speak to a student clinical psychologist to determine **targeted or specialist** allocation.

Based on initial screening, individuals will be categorised into a universal, targeted or specialist group and will receive an intervention based on the criteria identified in Table 2. **Table 2. Personalised Care Plans Delivered based on Needs Assessment**

	Universal	Targeted	Specialist

Exercise	
Home-based exercise (supported by regular phone/video calls with student physios/sports rehabilitation therapists);
 
Increasing frequency, intensity, and duration incrementally to achieve a minimum of 150 min per week of moderate/vigorous physical activity (MVPA)
 
In addition, 2 sessions of resistance training per week.
 
Sedentary time:replacing daily sittingtime with standing/moving time.
	
Delivered by student physios/sports rehabilitates group-based training (F2F - attend Hip-Hub sports injuries clinic at UoH or delivered virtually through Teams).
 
3 sessions per week (total home and facility-based sessions) of aerobic exercise training (minimum 20 minutes per session) (moderate or HIIT).
 
In addition, 2 sessions of resistance training per week.
 
Sedentary time:replacing daily sittingtime with standing/moving time (use activity diaries)
	
Delivered 1:1 in F2F Hip-Hub setting.
 
3 sessions per week (including x1 home session) aerobic training (minimum of 20 min per session at moderate intensity).
 
Additionally, if able, 2 resistance training sessions per week.

-----------------	---	---	--

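### The comorbidity check for supervised exercise comes after the DASI gate, so a patient with DASI above 34 who needs supervision is assigned unsupervised home exercise

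*Protocol*

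**What the plan says.** The Protocol section on screening and assessment for exercise, fitness and functional capacity has two labelled steps.

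- **Screening.** DASI is used to detect reduced functional capacity. "Patients with a DASI score > 34 are at low risk and will be assigned to" universal support, while "those with a DASI score <34 will be referred for an assessment".
- **Assessment.** An ISWT is performed. A distance below 475 m leads to the targeted tier and below 400 m to the specialist tier. As an alternative to the 400 m cut-off, "patients with a medical comorbidity that necessitates supervised exercise will be assigned to" the specialist tier.

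The Service Design text sets out the same order in general terms. "Those with no increased risk factors and with no increased surgical risk will receive" universal support, and "Further assessment will be undertaken for those requiring more than universal support".

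Table 2 defines what each exercise tier receives. Universal is "Home-based exercise (supported by regular phone/video calls with student physios/sports rehabilitation therapists"), rising to at least 150 minutes a week of moderate or vigorous activity, plus two resistance sessions a week. Specialist is delivered one-to-one and face to face, with three aerobic sessions a week, one of them at home, of at least 20 minutes at moderate intensity. Resistance training is added only if the patient is able.

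**The concern.** DASI measures functional capacity. A comorbidity that calls for supervised exercise is a separate reason for caution, and the Protocol treats it as one by making it an alternative to the walking-distance cut-off. A good capacity score therefore cannot rule it out. Yet the criterion sits behind the DASI gate, so patients above 34 are placed before anyone is told to look for it.

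The first thing at stake is safety. A patient who needs supervision by the Protocol's own criterion could be told to build up to moderate or vigorous activity at home with remote contact only. The second is consistency. Staff following the DASI rule and staff following the Service Design principle would put the same patient in different tiers. Adverse events and fidelity of delivery are both part of the primary feasibility assessment under Study Outcomes, so misplacement bears on what the trial sets out to measure.

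**Working it through.** The Protocol states no figure to reproduce. The check traces the allocation rule, then compares what the two tiers provide.

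**Tracing the rule for a patient with a comorbidity that needs supervised exercise**

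| Step | DASI above 34 | DASI below 34 |
|---|---|---|
| Screening | Universal support | Referred for assessment |
| Assessment | Not reached | Comorbidity criterion applies |
| Exercise tier | Universal (home, phone or video) | Specialist (one-to-one, face to face) |

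The two patients share the same comorbidity. Only the DASI score separates them.

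**Whether other text closes the gap**

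- *Exclusion criteria.* These remove "Any medical conditions for which moderate to vigorous exercise is contraindicated". A condition in which such exercise is allowed but should be supervised is different. If the exclusion covered both, the comorbidity criterion in the assessment step would have nobody to apply to.
- *Risk cap (Aims).* A score of 0 to 6 on an operative risk chart admits moderate-risk patients and is not a check on the need for exercise supervision.
- *Table 1.* The ISWT is listed for participants at 2 months from surgery, but the screening section does not use it to move patients with DASI above 34, and a walking test would not identify a comorbidity.
- *Clinical supervisor.* In the exercise screening section this role only judges whether a patient is unsuitable for the ISWT.
- *Oversight of students.* Professional guidance adds neither a comorbidity check nor in-person supervision of home exercise.

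**What an affected patient would receive (inputs from Table 2 and Table 1)**

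- Face-to-face aerobic sessions per week: Specialist 3 − 1 = 2; Universal 0.
- Minimum aerobic time per week: Specialist 3 × 20 = 60 minutes at moderate intensity; Universal builds to at least 150 minutes at moderate or vigorous intensity.
- Length of the programme, from 2 months before surgery (assumed 61 days) to the visit 2 to 10 days before surgery:
  - shortest: 61 − 10 = 51 days; 51 / 7 = 7.3 weeks
  - longest: 61 − 2 = 59 days; 59 / 7 = 8.4 weeks
- Specialist face-to-face aerobic sessions: 2 × 51/7 = 14.6 to 2 × 59/7 = 16.9, so about 15 to 17. Universal: 0.
- Share of the intervention arm per affected patient: 1 / 25 = 4%.

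**The case against.** The strongest reply is that the sections can be read together. Service Design limits universal support to people without increased risk factors, and a patient who needs supervised exercise hardly fits that description. The comorbidity clause carries no DASI condition of its own, and since the ISWT does not measure comorbidity, a stand-alone override is a natural reading. Patients are also seen in person at the 2-month visit, by students working under clinical professionals, so more than DASI is known before exercise starts. The group is probably small: the exclusions and the risk cap remove many higher-risk patients, and the detailed risk criteria are on a referral form that is not available here. Finally, the session counts compare schedules and do not measure harm, and even the Specialist tier includes one home session a week.

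Much of this stands. The intent is reasonably clear, the number affected is unknown and may be small, some cases may be caught informally, and the session counts are not an estimate of risk. None of it supplies the missing instruction. Service Design states a principle without a check to carry it out. If the comorbidity clause is meant to apply to everyone, the same patient has two assignments, universal by DASI and specialist by comorbidity, and no stated order of precedence. Either reading needs a correction.

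**Conclusion.** The concern holds. As the exercise screening section is laid out, the supervised-exercise criterion is reached only by patients with DASI below 34, and the result for others conflicts with the stated purpose of universal support. The fault should be fixed, but it is contained. It does not affect the sample size of 25 per group or the definition of any feasibility outcome.

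For an affected patient the difference is 0 against about 15 to 17 scheduled face-to-face aerobic sessions, together with a higher aerobic target. This assumes two months is 61 days, that the programme starts at once, and that Table 2 is delivered as scheduled. No number of affected patients is claimed, because the Protocol gives no frequency for DASI above 34 or for such comorbidities. This is a clinical allocation rule fixed in the Protocol, so a separate SAP would not be expected to settle it.

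**What to change.** In the exercise screening section, move the comorbidity criterion so that it is checked in every intervention patient before or alongside DASI. Suggested wording: *All intervention patients are checked for a comorbidity requiring supervised exercise; those who have one enter the Specialist exercise tier regardless of DASI score. All others follow the DASI pathway below.* The rest of the DASI, ISWT and Timed Up and Go pathway can stay as it is.

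Whether a short ISWT distance should also override a DASI above 34 is a clinical choice outside this point. Disagreements between the two could be reported descriptively for patients who complete the walk.

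The cost is one line of text and one check at the existing screening session, with no new test. The downside is that some patients may move to the more resource-intensive tier, at about 15 to 17 one-to-one aerobic sessions each. Those are patients the Protocol already says need supervision.
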